5.1.3 Coefficient of variation

The geometric coefficient of variation (CV) will be calculated using the following formula:

$$CV = 100\sqrt{e^{\text{var}} - 1}$$

where var = the variance from the log-transformed data.

5.2 Laboratory Evaluations

5.2.1 Clinical Chemistry

Items	Units
Albumin	$\mu\text{g/mL}$

Confidentiality Statement

Data and information contained in this document are considered to constitute trade secrets and confidential commercial information, and the legal protections provided to such trade secrets and confidential information are hereby claimed under the provisions of applicable law. No part of this document may be publicly disclosed without the written consent of Philip Morris Products S.A

Items	Units
Total protein	g/L
Alkaline phosphatase (AP)	nkat/L
Alanine aminotransferase (ALT)	µkat/L
Aspartate aminotransferase (AST)	µkat/L
Blood urea nitrogen (BUN)	mmol/L
Creatinine	umol/L
Gamma-glutamyl transferase (GGT)	U/L
Fasting Glucose	mmol/L
Lactate dehydrogenase (LDH)	µkat/L
Potassium	mmol/L
Sodium	mmol/L
Total bilirubin	µmol/L
Direct bilirubin	µmol/L
Total cholesterol	mmol/L
Triglycerides	mmol/L

5.2.2 Hematology

Items	Units
Hematocrit	-
Hemoglobin	g/L
Mean corpuscular hemoglobin (MCH)	pg/cell
Mean corpuscular hemoglobin concentration (MCHC)	g/L
Mean corpuscular volume (MCV)	fL
Platelet count	10^9/L

Confidentiality Statement

Data and information contained in this document are considered to constitute trade secrets and confidential commercial information, and the legal protections provided to such trade secrets and confidential information are hereby claimed under the provisions of applicable law. No part of this document may be publicly disclosed without the written consent of Philip Morris Products S.A.

Items	Units
Red blood cell (RBC) count	10 ¹² /L
White blood cell (WBC) count	10 ⁹ /L
Differential WBC count:	-
Neutrophils	
Basophils	
Eosinophils	
Lymphocytes	
Monocytes	

5.2.3 Urine Analysis

Items	Units
pH	-
Bilirubin	-
Glucose	-
Nitrite	-
Occult blood	-
Protein	-
Specific gravity	-

5.2.4 Clinical Risk Endpoints (CREs)

Items	Units
Apolipoprotein A1 **	g/L
Apolipoprotein B **	g/L
Hemoglobin A1C/Hemoglobin *	mmol/mol

Confidentiality Statement

Data and information contained in this document are considered to constitute trade secrets and confidential commercial information, and the legal protections provided to such trade secrets and confidential information are hereby claimed under the provisions of applicable law. No part of this document may be publicly disclosed without the written consent of Philip Morris Products S.A.

Items	Units
C Reactive Protein **	mg/L
HDL Cholesterol **	mmol/L
Homocysteine **	µmol/L
LDL Cholesterol **	mmol/L
Matrix Metalloproteinase 2 *	pg/mL
Matrix Metalloproteinase 9 *	pg/mL
11-dehydro-thromboxane B2 (11-DTX-B2) **	pg/mL
8-Epi Prostaglandin F2 Alpha (8-epi-PGF _{2a}) **	pg/mg creat
soluble inter-cellular adhesion molecule-1 (sICAM-1) **	ng/mL
Total Antioxidant Capacity *	umol/L
Fibrinogen **	umol/L
D-Dimer **	mg/L

* Measured up to protocol version 6

** Measured up to protocol version 7

5.3 Vital Signs

Items	Units
Systolic blood pressure	mmHg
Diastolic blood pressure	mmHg
Pulse Rate	beats/min
Respiratory Rate	breaths/min
Waist Circumference	cm
Body Weight	Kg
BMI*	-

Confidentiality Statement

Data and information contained in this document are considered to constitute trade secrets and confidential commercial information, and the legal protections provided to such trade secrets and confidential information are hereby claimed under the provisions of applicable law. No part of this document may be publicly disclosed without the written consent of Philip Morris Products S.A.

* BMI = Body Weight (kg) / [Baseline Height (m)]²

5.4 Physical Examinations

Items	Units
General appearance	-
HEENT (Head, eyes, ears, nose, throat)	-
Thyroid gland	-
Chest	-
Lungs	-
Gastrointestinal	-
Cardiovascular system	-
Neurologic	-
Skin	-
Musculoskeletal	-
Abdomen	-
Dentition	-

5.5 ECG

Items	Units
Heart rate	beats/min
PR interval	msec
QRS interval	msec
QT interval	msec
QTcB interval	msec
QTcF interval	msec

Confidentiality Statement

Data and information contained in this document are considered to constitute trade secrets and confidential commercial information, and the legal protections provided to such trade secrets and confidential information are hereby claimed under the provisions of applicable law. No part of this document may be publicly disclosed without the written consent of Philip Morris Products S.A.

5.6 ABI (Ankle-Brachial Index)

Items (left and right)	Units
Calculated ABI	-
Systolic pressure at the dorsalis pedis artery	mmHg
Systolic pressure at the posterior tibial artery	mmHg
Brachial arterial systolic pressure	mmHg

5.7 Product Use Categories

In addition to enrolled arms, subjects will be classified by product use categories. These will be defined based on the monthly average number of nicotine-containing products as self-reported in the diary.

More specifically, monthly for each subject, the average number over the entire month of cigarettes per day, IQOS per day, heat-not-burn products other than IQOS per day, e-cigarettes per day, smokeless tobacco pipe per day, smokeless tobacco per day, cigars/pipes/kiseru/shisha per day, and nicotine replacement therapy per day, will be determined as follows:

- If the subject answers 'every day' to the initial question related to a nicotine-containing product type, the number of days of use is set to 30. If the subject answers 'not at all' to this question, then the number of days of use is set to 0. If the subject answers 'some days', the number of days of use is set to the answer provided by the subject to the subsequent question on how many of the past 30 days the subject has used the product.
- The number of days of use is then multiplied by the number provided as answer to the question on the average number of products used per day by the subject (if the subject has 0 day of use, the subject does not need to answer that question and the average number of products used can be set to 0). The result of this multiplication is then divided by 30 to get an estimate of the average number of products used per day over the entire month.
- If the number of days is missing, or if it is not equal to 0 but the average number of products per day is missing, then the average number of products used per day over the entire month is set to missing.

Once the average number of products used per day over the entire month will be determined, all the available (out of 6) monthly averages collected between V2 and V3 will be summed up and divided by the number of non-missing monthly averages, and the result of this calculation

Confidentiality Statement

Data and information contained in this document are considered to constitute trade secrets and confidential commercial information, and the legal protections provided to such trade secrets and confidential information are hereby claimed under the provisions of applicable law. No part of this document may be publicly disclosed without the written consent of Philip Morris Products S.A.

will be assigned to V3 and represent the average number of products used per day over the previous 6 months. Similarly, all the available (out of 6) monthly averages collected between V3 and V4 will be summed up and divided by the number of non-missing monthly averages, and the result of this calculation will be assigned to V4. The process is repeated to obtain estimates of average number of products used per day over the previous 6 months for V5, V6, V7, and V8. If none of the 6 previous monthly averages is available, the average number of products used per day over the previous 6 months will be set to missing.

If a subject terminates the study early between V_i and V_{i+1} (where i represents any number between 2 and 7), the average number of products used per day over the previous 6 months will be set to missing at V_{i+1} .

For each subject, the following table will be filled, where each cell represents an average number of products used per day over the previous 6 months:

Product	V3	V4	V5	V6	V7	V8
Cigarettes/Roll-your-own cigarettes	Cig3	Cig4	Cig5	Cig6	Cig7	Cig8
IQOS	IQ3	IQ4	IQ5	IQ6	IQ7	IQ8
Heat-not-burn other than IQOS	HnB3	HnB4	HnB5	HnB6	HnB7	HnB8
E-cigarettes	EC3	EC4	EC5	EC6	EC7	EC8
Smokeless tobacco pipes	Stp3	Stp4	Stp5	Stp6	Stp7	Stp8
Smokeless tobacco	St3	St4	St5	St6	St7	St8
Cigars/Pipes/Kiseru/Shisha	Cpk3	Cpk4	Cpk5	Cpk6	Cpk7	Cpk8
Nicotine replacement therapy	Nrt3	Nrt4	Nrt5	Nrt6	Nrt7	Nr8

Using this table, the product use category for any subject will be determined as follows:

- A subject will be classified in the smoking abstinence product use category if all $Cigx < 1$, $IQx < 1$, $HnBx < 1$, $ECx = 0$, $Stpx = 0$, $Stx = 0$, $Cpk3 = 0$ for all $x = 3, 4, 5, 6, 7$, and 8 .
- A subject will be classified in the IQOS product use category if all $Cigx < 1$, $IQx \geq 1$, $HnBx < 1$, $ECx = 0$, $Stpx = 0$, $Stx = 0$, $Cpk3 = 0$ for all $x = 3, 4, 5, 6, 7$, and 8 .
- A subject will be classified in the CIG product use category if all $Cigx \geq 1$, $IQx < 1$, $HnBx < 1$, $ECx = 0$, $Stpx = 0$, $Stx = 0$, $Cpk3 = 0$ for all $x = 3, 4, 5, 6, 7$, and 8 .
- A subject will be classified in the dual-use product use category if all $Cigx \geq 1$, $IQx \geq 1$, $HnBx < 1$, $ECx = 0$, $Stpx = 0$, $Stx = 0$, $Cpk3 = 0$ for all $x = 3, 4, 5, 6, 7$, and 8 .

Confidentiality Statement

Data and information contained in this document are considered to constitute trade secrets and confidential commercial information, and the legal protections provided to such trade secrets and confidential information are hereby claimed under the provisions of applicable law. No part of this document may be publicly disclosed without the written consent of Philip Morris Products S.A.

- A subject will be classified in the ‘other’ product use category in all other cases not mentioned above.

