3.5.2 Evaluation Criteria

This is a descriptive study, designed to gain an understanding on the effect of complete switching from cigarettes to IQOS use compared to continued CIG smoking on AAA growth rate and disease progression. Dual use of IQOS on top of CIG will be also investigated.

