Female or male Japanese adult patients with diagnosed AAA meeting the following additional main inclusion criteria will be enrolled in the SC arm of the study:

8. Patient had completely quitted smoking and stopped the use of any other tobacco or nicotine-containing products for at least 6 months prior to the Screening and is still abstinent at Screening (V1) and at Baseline (V2). Smoking status will be verified based on a urinary cotinine test (i.e., cotinine < 100 ng/mL) (to be checked at V1 and V2).

Confidentiality Statement

Data and information contained in this document are considered to constitute trade secrets and confidential commercial information, and the legal protections provided to such trade secrets and confidential information are hereby claimed under the provisions of applicable law. No part of this document may be publicly disclosed without the written consent of Philip Morris Products S.A.

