5 DERIVED AND COMPUTED VARIABLES

5.1 Urinary Biomarkers

The concentration of NEQ in spot urine will be derived according to the formula below and considering the conversion factors described in Table 2. The concentrations reported for free nicotine and its five major metabolites will not be used individually as analysis variables.

$$\text{NEQ [mg/L]} = (\text{free nicotine [\mu mol/L]} + \text{nicotine-glucuronide [\mu mol/L]} \\ + \text{free cotinine [\mu mol/L]} + \text{cotinine-glucuronide [\mu mol/L]} \\ + \text{free } trans\text{-}3'\text{-hydroxycotinine [\mu mol/L]} \\ + \text{trans-3'-hydroxycotinine-glucuronide [\mu mol/L]}) \\ * 162.2[\mu g/\mu mol] / 1000 [\mu g/mg]$$

Table 2 Conversion factors from ng/mL into $\mu\text{mol/L}$

	Conversion factor from ng/mL to $\mu\text{mol/L}$
Nicotine	0.006164
Nicotine glucuronide	0.002955
Cotinine	0.005675
Cotinine-glucuronide	0.002838

Confidentiality Statement

Data and information contained in this document are considered to constitute trade secrets and confidential commercial information, and the legal protections provided to such trade secrets and confidential information are hereby claimed under the provisions of applicable law. No part of this document may be publicly disclosed without the written consent of Philip Morris Products S.A

Trans -3'hydroxycotinine	0.005202
Trans -3'hydroxycotinine-glucuronide	0.002715

Example: Free Nicotine [$\mu\text{mol/L}$] = Free Nicotine [ng/mL] $\times 0.006164$

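### SAP 5.7 sorts patients on separate six-month means below 1 per day, so low-level relapse and light dual use stay in the abstinence and IQOS categories

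*SAP*

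**What the plan says.** SAP 5.7 builds product use categories that are "defined based on the monthly average number of nicotine-containing products as self-reported in the diary". For each product, days of use in the month are multiplied by the number used per day, and the result is "divided by 30 to get an estimate of the average number of products used per day over the entire month". The months are then pooled into one value per visit window; for the first window, the "monthly averages collected between V2 and V3 will be summed up and divided by the number of non-missing monthly averages". The same is done for each window up to V8.

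The limits apply to these window means, one product at a time, in all six windows:

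- Smoking abstinence: "A subject will be classified in the smoking abstinence product use category if all $Cigx < 1$, $IQx < 1$, $HnBx < 1".
- IQOS: "A subject will be classified in the IQOS product use category if all $Cigx < 1", with an IQOS mean of at least 1 and other heat-not-burn below 1.
- Dual use: cigarette and IQOS means both at least 1, and other heat-not-burn below 1.
- Any pattern that fits no named category goes to 'other'. E-cigarette use, by contrast, must be exactly zero in every named category.

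SAP 3.5.2 describes the study as "designed to gain an understanding on the effect of complete switching from cigarettes to IQOS use" and adds that dual use will also be investigated. SC patients enter under the criterion "Patient had completely quitted smoking and stopped the use of any other tobacco or nicotine-containing products for at least 6 months". Protocol 6.3.2 then instructs them to use no tobacco or nicotine product at all, NRT excepted. Protocol 6.6.6 left the definition of adherence to the SAP, and SAP 8.3 (Table 3) refers to 5.7 for it.

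**The concern.** The labels suggest abstinence and switching, but the rule measures something looser. A six-month mean can absorb a whole month of smoking. Three separate limits below 1 can add up to almost 3 units a day. The dual-use category starts only when both means reach 1 in every window, so lighter dual use is recorded as IQOS use or as abstinence. The rule allows no e-cigarette use but does allow some cigarettes, and the SAP gives no reason for the difference.

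The stake is how the by-category outputs are read. SAP 9.5.1 and 9.5.2 repeat the growth rate, the diameter, time to event, incidence, the growth thresholds and the biomarker models by these categories. Protocol 2.1 states that smoking accelerates AAA growth. Residual smokers in the abstinence or IQOS group would therefore be expected to move that group's results towards smoking.

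**Working it through.** **Inputs.** All come from SAP 5.7, except the entry smoking level of more than 5 cigarettes per day (SAP 4.2.1, criterion 6). The plan states no figure on this point to reproduce.

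**Formulas.** Monthly mean = days × number per day / 30. Window mean = sum of the reported monthly means / number of reported months (at most 6). The category needs every window mean from V3 to V8 to meet the limits.

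**Patterns run through the rule**, with six months reported in every window and the pattern repeated in all six windows:

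| Use | Window mean | Category |
|---|---|---|
| 5 cigarettes/day for 1 month, none in the other 5 | 5/6 = 0.83 | abstinence; IQOS if IQOS mean ≥ 1 |
| 5.9/day for 1 month | 5.9/6 = 0.98 | the same |
| 6/day for 1 month | 6/6 = 1.00 | caught: leaves abstinence and IQOS |
| 1 cigarette on 29 of 30 days, plus 10 HeatSticks/day | 29/30 = 0.967 | IQOS |
| 1 cigarette every day, plus 10 HeatSticks/day | 30/30 = 1.00 | dual use |
| 1 cigarette and 1 HeatStick, each on 29 of 30 days | 0.967 each, 1.93 together | abstinence |
| The same plus 1 other heat-not-burn stick on 29 of 30 days | 0.967 each, 2.9 together | abstinence |

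**Limit of the rule.** Smoking r per day for L months of a window stays below the limit when L × r / 6 < 1, that is r < 6/L. The limit is 6 per day for one month, 3 for two months and 2 for three. For one month it lies just above the entry level: 5.5 per day gives 5.5/6 = 0.92 and is not caught. If a relapse at 6 or more per day affects only one window, the patient goes to 'other'.

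**Cumulative amounts.** The first pattern is 30 × 5 × 6 = 900 cigarettes over three years. The 29-of-30-day pattern is 29 × 36 = 1,044.

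**Missing months.** The denominator shrinks, so 5 per day for one month with one other month missing gives 5/5 = 1.00 and is caught. A relapse in a month without a diary entry is not seen at all.

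**Weight of one patient.** The documents give no category sizes. Protocol 4.4 reports 32 patients enrolled when the decision to stop recruitment was explained. One patient is 1/32 = 3% even if all 32 were in one category. With 10 in a category (an assumption) one patient is 10% and two are 20%.

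**The case against.** The case on the other side is substantial.

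- **The main comparison is not affected.** It is by randomized arm, SAP 4.3.3 presents the category analyses as additional, and the study is descriptive.
- **Residual use is visible.** SAP 9.4 tabulates and lists days of exposure and daily consumption of every product, by arm and by category. SAP 9.5.2.2 gives NEQ, Total NNAL, Total NNN and 2-CyEMA by category. A reader might infer that the categories are the SAP's only means of describing switching and dual use; these outputs show otherwise.
- **Heavier relapse is caught.** A reader might infer that any month-long relapse is hidden. That is true only below 6 per day with all six months reported.
- **Some tolerance is reasonable.** Monthly recall is imprecise, all six windows must comply, and the SC criterion quoted above governs entry rather than a later exposure label.
- **Biochemical checking.** SAP 5.1 says "The concentrations reported for free nicotine and its five major metabolites will not be used individually as analysis variables". A reader might take this as a bar on checking abstinence with cotinine. It restricts analysis variables when NEQ is derived and does not plainly forbid a data check. The 100 ng/mL entry cut-off also belongs to a site test (Protocol 7.7.3).

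All of this limits the impact. None of it changes who is placed in which category. The SAP gives no reason for a limit of 1 per day on a six-month mean and plans no stricter sensitivity rule.

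**Conclusion.** The point holds as a matter of the SAP's own arithmetic. With complete diaries, the abstinence and IQOS categories can include up to one month per window at just under 6 cigarettes per day, or one cigarette on 29 of 30 days throughout. Abstinence can also include light use of cigarettes and IQOS together. The by-category growth, event and biomarker outputs therefore do not isolate complete abstinence or complete switching, although SAP 3.5.2 names complete switching as the question.

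The documents do not show that any patient followed these patterns, nor how far under one cigarette a day changes AAA growth. A reader might infer a bias of known size in the growth rates; only its expected direction can be argued. This is a low-cost improvement to a supplementary analysis and does not undermine the comparison by arm.

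**What to change.** Amend SAP 5.7 before database lock, as SAP section 1 allows.

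1. **Main rule.** For smoking abstinence, require Cigx + IQx + HnBx < 1 in each window and no single monthly average of 1 or more for any of the three. For IQOS, require no month with a cigarette average of 1 or more.
2. **Strict sensitivity classification from the monthly diary.**
   - Complete abstinence: zero days of use of every tobacco or e-cigarette product in all reported months, NRT allowed.
   - Complete switcher: IQOS use, with zero days of cigarettes and of other heat-not-burn products.
   - Any dual use: at least one month with both cigarettes and IQOS.

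   Repeat the by-category growth-rate, diameter and biomarker summaries with it.

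Both parts are needed. One cigarette on 29 of 30 days gives a monthly average of 0.967 and passes the monthly limit, so only the strict classification removes it. Part 1 also leaves the dual-use rule as it is: the patients it removes go to 'other', and only part 2 counts light dual use.

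The cost is SAP wording and a little programming on data already collected. The strict groups will be smaller, and 'other' will be larger under the main rule. A cotinine check is optional and only a descriptive flag. The SAP would have to name the laboratory fraction to compare (free cotinine, its glucuronide or both), because the 100 ng/mL cut-off comes from the site test.

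### SAP 5.7 fixes the cigar/pipe/kiseru/shisha test at V3 (Cpk3) in all four named product-use categories; this is almost certainly a slip for Cpkx and should be corrected before the derivation is relied on

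*SAP*

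**What the plan says.** SAP 5.7 (Product Use Categories) turns the monthly diary into a table per patient, with one row per product group and one column per visit from V3 to V8. Each cell is the average daily use over the six months before that visit. The row "Cigars/Pipes/Kiseru/Shisha" has its own cell at every visit, Cpk3 to Cpk8.

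Four definitions then use the table:

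- "A subject will be classified in the smoking abstinence product use category if all $Cigx < 1", and so on.
- "A subject will be classified in the IQOS product use category if all $Cigx < 1", and so on.
- "A subject will be classified in the CIG product use category if all" its conditions hold.
- "A subject will be classified in the dual-use product use category if all" its conditions hold.

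All four finish with the same string: "ECx = 0$, $Stpx = 0$, $Stx = 0$, $Cpk3 = 0$ for all $x = 3, 4, 5, 6, 7$, and 8" (the dollar signs are typesetting marks). The part at issue is its end: "Cpk3 = 0$ for all $x = 3, 4, 5, 6, 7$, and 8". Anyone who meets none of the four goes to the "product use category in all other cases not mentioned above", that is, to *other*.

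SAP 8.1 has the FAS analysed by enrolled arm and also by product-use category. SAP 9.5.1 to 9.5.3 repeat this double grouping for growth rate, AAA diameter, time to event, incidence rates, rapid growth, cardiovascular risk factors, biomarkers of exposure and the additional analyses.

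**The concern.** The rule allows no cigar, pipe, kiseru or shisha use in any named category, but as printed it enforces this only for the average assigned to V3. Cpk4 to Cpk8 are derived and never used in the classification. No other part of the SAP or protocol corrects this.

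The categories matter because the evaluation criterion in SAP 3.5.2 and protocol 12.6 concerns complete switching, with dual use also of interest. The by-arm analyses keep patients in their randomised arm whatever they use, so the categories are the SAP's means of separating patients by actual use. If the rule is coded as printed, the named categories could contain patients who took up another tobacco product, some forms of it smoked, during the last two and a half years. All four are exposed: CIG and dual use as much as IQOS and abstinence.

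**Working it through.** **No figure to reproduce.** The plan gives no number on this point. The check compares the terms of the rule and then applies it under both readings.

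**Step 1. Compare the terms.** Inputs are the table and the four definitions in SAP 5.7.

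| Product group | Cells derived | Term in all four definitions | Visits tested |
|---|---|---|---|
| Cigarettes | Cig3–Cig8 | Cigx | V3–V8 |
| IQOS | IQ3–IQ8 | IQx | V3–V8 |
| Other heat-not-burn | HnB3–HnB8 | HnBx | V3–V8 |
| E-cigarettes | EC3–EC8 | ECx | V3–V8 |
| Smokeless tobacco pipes | Stp3–Stp8 | Stpx | V3–V8 |
| Smokeless tobacco | St3–St8 | Stx | V3–V8 |
| Cigars/pipes/kiseru/shisha | Cpk3–Cpk8 | **Cpk3** | **V3 only** |

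NRT has a row in the table but is not tested in any definition. Across the four definitions, 6 × 4 = 24 terms carry x and 4 carry the fixed 3. The clause that runs x from 3 to 8 cannot act on a term that contains no x.

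**Step 2. Size of the gap.** Cpk3 covers V2 to V3, one of six half-year intervals. Unchecked: 6 − 1 = 5 intervals, or 5 × 6 = 30 of 36 months (30/36 = 83%).

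**Step 3. Apply both readings.** Assume complete diaries and constant use of the main product: none, IQOS only, cigarettes only, or both. Let cigar/pipe use start in the interval ending at a given visit and continue to V8.

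| Start of cigar/pipe use | Literal rule (Cpk3 = 0) | Running index (Cpkx = 0, x = 3 to 8) |
|---|---|---|
| Never | category kept | category kept |
| V3 | *other* | *other* |
| V4, V5, V6, V7 or V8 | category kept | *other* |

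The last row holds for all four profiles: 4 profiles × 5 start points = 20 combinations. All 20 keep their category under the literal rule, and all 20 move to *other* under the running index.

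**Step 4. All on/off patterns.** For a constant IQOS user there are 2^6 = 64 patterns of cigar/pipe use over V3 to V8. The literal rule leaves 2^5 = 32 in the IQOS category, namely every pattern with no use at V3. The running index leaves 1, the pattern with no use at all. These are counts of logical patterns, not estimates of how often they occur.

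**The case against.** The strongest reply is that this is a notation slip with an obvious meaning. Every neighbouring term carries x, each definition ends by running x from 3 to 8, and Cpk4 to Cpk8 would otherwise serve no purpose in the classification. The same table has another slip: the last NRT cell is labelled Nr8 where the pattern calls for Nrt8. The documents contain no program for this derivation, so nothing shows that the literal rule has been or will be coded. This stands, and it makes the consequence conditional. It does not remove the need to correct the text. Protocol 12.1 requires the analyses in the signed SAP to be carried out as described, so one programmer could code Cpk3 and another Cpkx from the same document.

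An error in extracting text from the PDF is also possible with subscripted symbols. It is unlikely, because the string is the same four times while the x survives in all 24 other terms. A glance at the signed SAP settles it.

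Later use would also not be hidden. SAP 9.4 tabulates days of exposure and daily consumption of these products for V3 to V8 and overall, by arm and by category, and lists product use and category. This stands as a safeguard: the use would be seen, though nobody would be reclassified.

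A reader might infer that every FAS endpoint is contaminated. The documents do not support that. SAP 4.3.3 calls the analyses by actual use additional, and SAP 9.5.1.1 defines the primary comparison by randomised arm. The summaries of adverse events, laboratory values, vital signs and ECG are grouped by arm only. SAP 8.3 does point to section 5.7 when it lists product adherence as a major deviation, but it does not make the category the ground for exclusion, and FAS membership in SAP 8.1 does not depend on it.

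A reader might also divide the 32 patients in protocol 4.4 by three and conclude that one misclassified patient is about a tenth of a category. That has no basis. The 32 is a total at one time point with no split by arm, the SC arm has no stated allocation, and category sizes are not arm sizes.

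**Conclusion.** The text is wrong as written, and it is an operative rule rather than background. It is best described as a typographical error with a conditional consequence. If Cpk3 is programmed literally, cigar/pipe/kiseru/shisha use that starts after V3 does not move a patient to *other*, in any of the four named categories. The by-arm primary comparison is not affected; the exposure is confined to outputs by product-use category.

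The size in patients is unknown and may be zero, because neither document reports any use of these products during the study. The conclusion rests on two assumptions: that the printed SAP shows Cpk3 as quoted, and, for any actual effect, that the program follows the print. The documents do not support the firmer statement that patients will be misclassified. The point is minor, but it costs almost nothing to correct.

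**What to change.** In each of the four definitions in SAP 5.7, replace Cpk3 = 0 with Cpkx = 0, so that the existing clause for x = 3 to 8 covers it. Correct Nr8 to Nrt8 at the same time. Then check that the programmed derivation tests all six Cpk cells.

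SAP section 1 allows amendments before database lock. If the database is already locked, state in the CSR which reading was programmed and document the correction, noting any patient whose category changes.

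The cost is one character in four lines plus a short program check. No new data are needed, and no design element or by-arm analysis changes.
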